Notably, this team has identified factors that contribute to Black women's uptake of GCT. In preliminary studies, researchers found that self-efficacy in making decisions about GCT and medical mistrust were associated with GCT uptake. Low knowledge among Black BC survivors at risk of HBOC has also been found. Anticipated negative emotions to GCT have been associated with lower uptake. Similar studies suggest that Black women report emotions related to fear of being singled out and the fear of being hopeless. Because most interventions have

focused solely on knowledge or access, the proposed study makes a considerable shift in the field by additionally targeting emotions and ambivalence and developing a media-based risk communication tool.

Guided by two evidenced-based theories and preliminary data, this was a two-phased mixed methods study. In Phase I (months 1-7), formative research and preliminary data were used to develop the script for the GCT video. The script was reviewed by GCT experts (n=4) and piloted in two focus groups (n=16), followed by a staged reading to make final refinements. In Phase II (months 8-24), a two-arm randomized trial (RCT) to compare GCT uptake and psycho-social outcomes between 50 at-risk Black women receiving printed Susan G. Komen developed GCT literature (control group) (n=25) or a tailored YouTube video intervention (n=25) was be conducted. All women were referred to an appointment scheduler who assisted them with making an appointment with a genetic counselor. Participants completed a baseline survey and follow-up assessment. The primary outcome was genetic counseling uptake, and receipt testing at 3 months was explored. Specific aims are to:

Aim 1. Develop a YouTube video using formative data for Black women at risk for HBOC.

Aim 2. Evaluate the efficacy of the intervention by comparing outcomes between women in the YouTube intervention arm vs. the control group arm. H.2.1. Women in the intervention group (vs. control group) had higher genetic counseling uptake. H.2.2. Women in the intervention group (vs. control group) was report higher knowledge, higher self-efficacy, higher endorsement of positive attitudes, and positive anticipated emotions about GCT. H.2.3. Most women ($\geq 75\%$) were satisfied with the experimental intervention.

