Enhancing GCT in at-risk populations is a national priority. Given trends toward panel testing and other genomic advances, there is potential for existing disparities to widen. Findings inform new strategies for behavioral interventions for Black women and a larger trial. If successful, the intervention could be easily disseminated, broadening its reach to affected and unaffected women.

This study meets the Healthy People 2020 goals to enhance GRCA in at-risk populations, and the national priorities to increase diversity in genetics research participation and incorporate emotions into cancer research. Findings informed new strategies for behavioral interventions targeting African Americans in a larger trial.

Participation Criteria

Inclusion Criteria:

- Must be at least 18 years of age
- Must be at high risk for hereditary breast or ovarian cancer
- Must identify as Black/African American
- Must be a woman
- Referred to a genetic counselor for the purpose of being at high risk of carrying a hereditary breast and/or ovarian cancer mutation

Improving Uptake of Genetic Cancer Risk Assessment in African American Women - Video

Genetic Counselors:

- Must be at least 18 years of age
- Must be qualified
- Must be approved by the PI

Exclusion Criteria:

- Under the age of 18
- Race other than Black/African American
- Do not have a high risk for hereditary breast or ovarian cancer

Genetic Counselors:

- Under 18
- Not qualified
- Not approved by the PI

Participant Group/Arm	Intervention/Treatment
No Intervention: Fact Sheet Arm Komen print materials about genetic counseling and testing will be given to women.	
Active Comparator: YouTube Video Arm Participants in this arm will receive the culturally tailored video either via a YouTube link or a DVD.	
Behavioral: YouTube Video Arm
 
• Participants (n=25) watched a 20-minute YouTube video that described the genetic counseling and testing process and risk/benefit information in a culturally relevant format. Participants completed pre and post-assessments. After the session, participants interested in pursuing genetic counseling and testing services were referred to a patient navigator who navigated participants to identify no-cost or low-cost services.

What is the study measuring?

Outcome Measure	Measure Description

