Rate of genetic counseling and testing uptake.	Our primary outcome was for participants to receive genetic testing and counseling. Investigators were able to see if a participant had scheduled a genetic testing appointment within the VCU Health appointment system.

Secondary Outcome Measures

Outcome Measure	Measure Description	Time Frame
Knowledge Scale - Genetic counseling and testing knowledge.	The investigators tested general knowledge about hereditary breast and ovarian cancer	Within one hour before the intervention and within one hour post-intervention.
Self-efficacy Scale	The investigators tested self-efficacy in genetic counseling services.	Within one hour before the intervention and within one hour post-intervention.
Emotional Ambivalence Scale	The investigators tested the emotional ambivalence about participating in genetic counseling services.	Within one hour before the intervention and within one hour post-intervention.

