## Statistical Analysis Plan

**Data Analysis, Statistical Design and Power.** This study is designed to evaluate feasibility and to estimate effect sizes for a future planned confirmatory RCT. As such, the sample size calculation is based on practical considerations. van Belle and Julious have both recommended a minimum sample size of twelve per group for pilot studies. This is based on the fact that the precision of the estimate of the mean and variance greatly increases up to a sample size of twelve at which point the decrease becomes less dramatic. Although these recommendations were based on continuous outcomes, the same logic applies to binary outcomes as the square root of N also appears in the denominator for the test of proportions. With a sample size of 25 per group we will have an adequate sample to estimate the difference in the proportion of participants who obtain GT between groups. No attrition is expected for the primary outcome as patient records will be used to determine if participants seek GT.

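### The primary outcome is defined as counseling and testing received, but the ascertainment described is a scheduled genetic testing appointment at VCU Health; complete records do not close that gap

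*SAP*

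**What the plan says.** The documents describe the primary outcome in four ways.

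- Protocol, What is the study measuring?, definition: "Our primary outcome was for participants to receive genetic testing and counseling".
- Same entry, how it was seen: investigators could tell whether a participant "had scheduled a genetic testing appointment within the VCU Health appointment system".
- Protocol, Detailed Description: "The primary outcome was genetic counseling uptake". Receipt of testing at 3 months is named there as exploratory.
- SAP, Data Analysis, Statistical Design and Power: the aim is to "estimate the difference in the proportion of participants who obtain GT between groups", yet the following sentence reads "No attrition is expected for the primary outcome as patient records will be used to determine if participants seek GT". The SAP text available does not expand GT.

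Three other statements bear on how uptake could be recorded.

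- Detailed Description, support: "All women were referred to an appointment scheduler who assisted them with making an appointment with a genetic counselor".
- Arm table, video row only: interested participants "were referred to a patient navigator who navigated participants to identify no-cost or low-cost services".
- Detailed Description, data collection: "Participants completed a baseline survey and follow-up assessment". Nothing says whether the follow-up assessment asks about uptake.

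**The concern.** A record for every woman guarantees a value for every woman. It does not guarantee that the value describes the event the trial set out to measure. Here the described record differs from the stated endpoint in two respects: scheduling is not receipt, and a testing appointment is not a counseling visit. A third gap is conditional: a single health system's appointment record cannot show a visit made elsewhere.

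The SAP gives the study's purpose as estimating effect sizes for a confirmatory trial, and the Study Overview looks ahead to a multi-center one. If that trial counts counseling received and this one counted testing appointments booked, the rates and the difference carried forward describe a different outcome. If the later trial uses the same kind of scheduling measure, the planning inputs remain usable.

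**Working it through.** **1. The plan's own figures.** The SAP gives 25 women per group and no attrition. Inflation for attrition is 25/(1 − 0) = 25, so the two agree. No alpha, power, control rate or target difference is stated, so nothing further can be reproduced. One woman is 1/25 = 4 percentage points of her arm's rate.

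**2. The texts side by side.**

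| Place | Service | Event |
|---|---|---|
| Outcome table, definition | testing and counseling | received |
| Outcome table, ascertainment | testing | scheduled, VCU Health |
| Detailed Description | counseling primary, testing exploratory | uptake |
| SAP, quantity to estimate | GT | obtained |
| SAP, use of records | GT | sought |

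The ascertainment row matches neither the definition nor the Detailed Description. No attendance check is described.

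**3. Unattended bookings.** The documents give no uptake or no-show rates. Assume true received uptake of 30% (control) and 50% (video), a 20-point difference with a risk ratio of 1.67.

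*Model A: a share s of bookings in each arm is unattended.* Recorded rate = p/(1 − s).
- s = 0.10: 0.30/0.90 = 33.3% and 0.50/0.90 = 55.6%; difference 22 points.
- s = 0.20: 0.30/0.80 = 37.5% and 0.50/0.80 = 62.5%; difference 25 points.

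The risk ratio stays at 1.67 in both cases because the error is proportional.

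*Model B: a share F of women not counseled has a booking, equal in both arms.* Recorded rate = p + (1 − p)F.
- F = 0.10: 0.30 + 0.07 = 37% and 0.50 + 0.05 = 55%; difference 18 points, risk ratio 0.55/0.37 = 1.49.
- F = 0.20: 0.30 + 0.14 = 44% and 0.50 + 0.10 = 60%; difference 16 points, risk ratio 0.60/0.44 = 1.36.

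The sign reverses because Model A implies unequal false-positive rates among women not counseled. At s = 0.20 these are 0.075/0.70 = 10.7% in control and 0.125/0.50 = 25% in video. The documents do not favor either model.

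**4. Counseling elsewhere (conditional).** If a share o of true uptake is not seen, the recorded rate is p(1 − o). With o = 0.20 in both arms: 24% versus 40%, 16 points. With o = 0.20 in the video arm only: 30% versus 40%, 10 points.

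**5. Bounds in whole women.** Assume recorded counts of 6/25 and 10/25, a difference of 4/25 = 16 points.
- Up to k unattended bookings per arm: (4 − k)/25 to (4 + k)/25. For k = 1, 12 to 20 points; for k = 2, 8 to 24.
- Up to k women per arm misclassified in either direction: (4 − 2k)/25 to (4 + 2k)/25. For k = 1, 8 to 24 points; for k = 2, 0 to 32. These extremes need opposite errors in the two arms.

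**6. Against random error.** The 95% interval half-width at 30% versus 50% is 1.96 × √(0.30 × 0.70/25 + 0.50 × 0.50/25) = 0.266, about 27 points. The shifts in steps 3 and 4 are all smaller than this.

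**The case against.** The SAP sentence concerns attrition and makes no claim about accuracy. That stands: a reader might infer that the sentence is false, and the documents do not support this. The mismatch lies in the protocol's outcome entry; the SAP sentence merely leaves it unaddressed.

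The protocol says what investigators could see, not that scheduling was the whole scoring rule. The SAP's patient records could include attendance, and part of the SAP text was not available to this review. This also stands, so the error is conditional on scheduling alone being scored. The definition and the described ascertainment still need to be reconciled.

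A reader might infer that women in the video arm were sent outside VCU Health and that the trial is therefore biased against the video. The text does not carry that. The low-cost services are not placed inside or outside VCU Health, and no woman is shown to have gone elsewhere. The navigator sentence sits in a table column that is blank for the control arm, which may be layout only, and the Detailed Description gives all women a scheduler.

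A reader might equally infer that missed visits inflate the effect. Model B shows that they can shrink it.

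Finally, in a pilot of 25 per arm the shifts are smaller than random error. True, but a confidence interval shows random error and does not show a mismeasured outcome, and more women would not remove it.

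**Conclusion.** The concern holds as a mismatch between the stated primary outcome and its described ascertainment: received against scheduled, and counseling against testing. It rests on the text alone. Whether any woman was misclassified depends on an unstated scoring rule. Counseling outside VCU Health is a secondary possibility, and a difference between arms in support or in capture is not established.

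Size and direction of bias are unknown. Under assumed true rates of 30% and 50%, unattended bookings at 10% or 20% move a 20-point difference to anywhere from 16 to 25 points depending on the model. The consequence for planning arises only if the confirmatory trial measures uptake differently. The point is worth fixing because it concerns the primary outcome and most of the remedy is wording.

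**What to change.** 1. Score the primary outcome as a genetic counseling visit attended within a stated window, for example the 3 months already used for testing. Read it identically in both arms from VCU Health records, and report testing separately.
2. If attendance cannot be read, label the outcome 'genetic testing appointment scheduled at VCU Health' and do not report it as counseling received.
3. Add a short two-sided bounding table covering unattended visits and uptake elsewhere. If the follow-up assessment already holds an uptake item, use it as a sensitivity analysis only, since non-response may differ by arm.
4. Amend the SAP sentence to say that records give every woman a value but do not show uptake elsewhere.
5. Reconcile the Detailed Description and the arm table on whether both arms had the same scheduler or navigator support.

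Cost: a check of attendance in existing records, if they hold it, a table of a few rows, and changes of wording. The recorded uptake rate may fall. Much of the protocol is in the past tense; if data collection is complete, the redefinition must be declared as post hoc and the scheduling measure reported beside it.
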